**NCT05872581**

**Date: 1 May 2023**

## Background

The ongoing COVID-19 pandemic has posed serious threats to public health worldwide. Although children have mild symptoms, they have been found to more likely transmit the virus within the household than the other age groups. The importance of hand hygiene cannot be underestimated in both healthcare and community settings (Allegranzi et al., 2011; Mathur, 2011). The promotion of hand hygiene is the best practices in preventing health care-associated infection (WHO, 2009). It has been estimated that hand hygiene could reduce over 500 000 attributable deaths per year. It was found that the annual economic impact of health care-associated infection in the US was approximately US\$6.5 billion in 2004 (WHO, 2009) and every US\$1 spent on hand hygiene promotion could result in a US\$23.7 benefit (Chen et al., 2011). Education plays a key role in setting a good practice base in hand hygiene.

The traditional training methods for nursing students include in-class lecture and practical, but students seldom receive individualized instructions and feedbacks due to limited manpower and facilities. Hence, there is an urgent need of designing an automated and individualized education program. This study aims to design and test a multicomponent education program of hand hygiene in nursing students. Specifically, this program has two components: 1) training videos according to the WHO guidelines on hand hygiene in health care (<https://polyu.ap.panopto.com/Panopto/Pages/Viewer.aspx?id=f3973cee-bcfb-48fd-a306-b6893dacaabd>); 2) a hand scanner used for students to immediately visualize the missing spots of hand hygiene.

This study has the following specific objectives:

- 1) conduct a randomized controlled trial (RCT) to test the effectiveness of this program on knowledge and practice of hand hygiene in nursing students;
- 2) evaluate the effects of each component and collect feedbacks from participants.

If demonstrated effective, this program can be integrated into the curriculum of nursing students as an e-learning approach. In future, this system can also be used at point-of-care for real-time monitoring and audit of healthcare workers in other healthcare settings.

## Methods

### *Study design*

This is a four-arm RCT.

### *Subject recruitment*

We will recruit all year one nursing students from the Bachelor of Nursing and Bachelor of Mental Health Nursing program in School of Nursing (total number is approximately 280) during June to July 2023. The participants will subscribe a timeslot of training sessions (each session has 3 participants). All participants who attend the same session will be assigned to the same group by cluster randomization. A statistician will assign the groups in advance by a random number generator. The participants will not be informed about their group before arriving the study site (the Squina International Centre for Infection Control in PolyU).

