### **Randomization, allocation concealment, and blinding**

Participants will be randomly assigned to the intervention groups or control group through a process of randomization performed by a statistician who will not be involved in subject recruitment. The participants will be blinded. The RAs involved in subject recruitment and the IPC experts who judge the quality of hand hygiene will be blinded to the groupings. The RAs and student assistants involved in hand hygiene video recording at the study site will not be blinded because they will be giving instructions to the participants.

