### **Ethical consideration**

The effect of exposure to UV-A light is similar to outdoor exposure to sunlight. It is anticipated that the study will not pose any physical or psychological harm to the participants. The contact details of either the ethical or the research in-charge personnel are clearly written in the information sheet.

Explanation of the study will be given to participants who are interested in participating in the study. Participants will also be given the opportunity to ask our project personnel questions. Furthermore, the information sheet including the purpose of the study, confidentiality of the data, and rights of the participants, will also be provided to the participants. The contact details of either the ethical or the research in-charge personnel are clearly written in the information sheet. If they agree to participate in the study, they are required to sign the consent form. Their participation is on a voluntary basis, they have the right to withdraw from the study at any time if they want to without consequence.

All the collected data will be kept confidentially, and only the research personnel can access and handle the data. No personal information of the participants will be collected except the student ID number.

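### Does assigning about 93 sessions to four arms by a random number generator leave the arm sizes, and so the precision, badly unsecured?

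*Protocol*

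**What the plan says.** Under Subject recruitment, the protocol plans to enrol a whole first-year intake ("total number is approximately 280"). Students book slots: "The participants will subscribe a timeslot of training sessions (each session has 3 participants"). The unit of allocation is explicit: "All participants who attend the same session will be assigned to the same group by cluster randomization". The method is given as "A statistician will assign the groups in advance by a random number generator". On concealment it adds: "The participants will not be informed about their group before arriving the study site".

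The section Randomization, allocation concealment, and blinding returns to the subject in general terms: "Participants will be randomly assigned to the intervention groups or control group through a process of randomization performed by a statistician", who takes no part in recruitment. Recruiting research assistants are blinded. Site staff are not: "The RAs and student assistants involved in hand hygiene video recording at the study site will not be blinded".

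Neither section gives an allocation ratio, a restriction such as blocking, or a target number of sessions per arm. The protocol contains no sample-size or power calculation against which an arm size could be judged.

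**The concern.** Four arms share about 93 clusters, roughly 23 each. If each session were assigned independently with probability 1/4, nothing would hold the arms near 23. Group D is the comparator for Groups A, B and C, so a small Group D would weaken three contrasts at once. The pool is one year's intake and "Their participation is on a voluntary basis", so sessions lost to imbalance could not easily be replaced, and lower enrolment would make the relative imbalance larger. The list is drawn up before the sessions run, so a later analysis plan could not restore balance.

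There is also an apparent clash over the unit: one section randomises sessions, while the other speaks of participants being randomly assigned. A reader who saw only the second might take the trial to be individually randomised.

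At stake would be precision, and perhaps clarity. Bias is not at issue, because unrestricted randomisation is a valid method.

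**Working it through.** **1. What the text commits to.** The generator sentence fixes who makes the list (a statistician), when (in advance) and with what tool (random numbers). It does not fix the form of the list. Permuted blocks, a shuffled list with a set number of sessions per arm, and independent draws all come from a random number generator. The imbalance follows only from the last of these, which the protocol does not name.

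**2. Inputs for the unfavourable reading.** From the protocol: about 280 students, 3 per session, 4 arms. Assumed: equal allocation probabilities, full sessions, full enrolment.

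- Sessions: 280/3 = 93.3, taken as 93. Per arm: 93/4 = 23.25.
- SD of one arm's count: √(93 × 0.25 × 0.75) = 4.18. 95% range: 15 to 32 sessions.
- Gap between largest and smallest arm: mean 9.9 sessions, 95th percentile 17 (400,000 multinomial draws).

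The protocol states no figure of its own to reproduce.

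**3. Cost for a contrast named beforehand.** With equal session sizes the intracluster correlation cancels, so the variance relative to exact balance is

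R = (1/k₁ + 1/k₂) / (2/23.25), where k is the number of sessions in an arm.

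Over the draws, R has mean 1.035, median 1.019 and 95th percentile 1.255. The standard error rises by 1.6% on average and by 12% at the 95th percentile.

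Two worked cases show why a wide gap in arm sizes need not be costly:

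- Arms of 19 and 28 sessions, the median smallest and median largest arm: (1/19 + 1/28)/(2/23.25) = 0.08835/0.08602 = 1.027.
- Two arms of 28 each: (2/28)/(2/23.25) = 23.25/28 = 0.83, which is more precise than exact balance.

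R falls below 1 in about 43% of lists, because the two arms being compared sometimes receive more than half of the sessions.

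**4. Cost for a component effect.** The protocol's second objective is to evaluate each component, and Groups A to D form a two-by-two layout (scanner feedback yes or no, video yes or no). For such a main effect the ratio is Σ(1/kᵢ) / (16/93), with mean 1.035 and 95th percentile 1.095. The protocol does not say which contrast is primary. On this one the tail is much shorter.

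**5. The larger figures.** The least precise of the three contrasts with Group D has mean R = 1.13 and 95th percentile 1.33. This is a maximum picked after seeing the draw, so it does not describe a contrast chosen in advance.

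**6. In power terms (illustrative).** Assume a two-sided 5% test and an effect that gives 80% power under exact balance. Simple randomisation gives 78.8% on average for a pre-chosen pair (5th percentile 70.6%). A 23/23/23/24 split gives 79.6% for a 23-against-23 comparison. The average difference is 79.6 − 78.8 = 0.8 percentage points.

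**7. Lower enrolment (assumed).** At 70% (65 sessions), mean R is 1.05; at 50% (47 sessions), 1.08, with a 95th percentile of 1.43. The average cost remains single-digit.

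**8. What blocking would cost.** With permuted blocks of 4 and 8 as an example, arms hold 22 to 24 sessions and mean R is 1.001. But someone who saw every earlier allocation could guess the next correctly about 48% of the time (45% with blocks of 8 and 12), against 25% under simple randomisation. Withholding the block sizes hardly lowers that rate. The gain also presumes full sessions: blocking balances sessions, not students, and consent is signed only at the site visit.

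**9. The unit.** The recruitment section names the session as the cluster. The later section says that participants end up in groups by a random process run by a statistician, which is also true when they are allocated by session. It names no different unit, so the two sections are compatible.

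**The case for a change.** The strongest case for the concern is that sequence generation is conduct, not analysis. It happens before the first session, the protocol has a section devoted to it, and no analysis plan can repair an unlucky list. Stating a 1:1:1:1 ratio and a restriction would need no extra students or measurements. The imbalance figures are correct on their assumptions, and an unlucky list could be felt: in the worst 5% of lists a given pairwise variance is at least 25% higher. The predictability argument is also limited, because students book before they know their group, recruiters are blinded and the list is fixed in advance.

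Much of this stands as description. The protocol would be fuller with the ratio written down, and the later section would be tidier if it named the session. But the case rests on a reading that the text does not adopt. On that reading it shows a modest loss between two valid methods, with some gain in unpredictability on the other side. It identifies no incorrect statement, no contradiction and no choice that harms the trial. Whether the analysis accounts for session is a separate matter that may properly sit in the analysis plan, which is not at hand.

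**Conclusion.** The concern does not hold. The protocol leaves open a detail that the statistician preparing the list can settle sensibly, and its wording is compatible with a balanced list. If the list were unrestricted, the trial would remain unbiased. At 93 sessions a pre-chosen pairwise contrast would lose 3.5% of variance on average (95th percentile 25%), and a component main effect the same on average (95th percentile 9.5%). These figures assume equal allocation probabilities, sessions of three and full enrolment; the averages rise to about 5% and 8% at assumed enrolment of 70% and 50%. The difference in wording between the two sections is editorial, since the session is already named as the cluster. No change to the protocol is required on this point.

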## Protocol

Date 1 May 2023

### *Pre-intervention assessment*

During the site visit, the participants will sign a consent form first and be asked to fill in a questionnaire on knowledge and practice of hand hygiene (attached in Appendix).

Participants will need to put fluorescent powder on both of their hands, and hold hands under ultraviolet (UV) light (wavelength: 365nm) to take digital image of hands. Participants will then perform hand washing using liquid soap without any instructions (1st HW attempt). The camera installed above the hand-wash basins will take videos of both hands (no face nor other parts of the body) during this procedure. After washing hands, participants will hold hands under UV light again to take digital image of hands, and will need to scan fluorescent powder remained on their hands in a hand scanner (The Semmelweis ScannerTM). The digital images of hands and the recorded hand washing videos will be used to train the AI algorithms for automatic image processing and assessments. Two IPC experts will judge the quality of hand hygiene in these images/videos, which will be adopted as ground truth in image processing. The percentage of fluorescent gel residual on hands shown in the hand scanner will be used as an objective assessment for efficacy of hand washing in individual participants.

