### *Intervention and control groups*

#### Group A (Hand scanner instant feedback)

Participants will be informed about their hand scanner results of the first HW attempt to get individualized feedback about their hand wash performance. But no training video is provided.

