#### Group B (Video training)

Participants will watch a training video about the 7 steps of hand washing after the first HW attempt, but they will not be informed about their hand scanner results.

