#### Group D (Control group without intervention)

Participants will not be informed about the hand scanner results in the first HW attempt and no training videos will be provided.

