### *Post-intervention assessment*

The participants will take the second HW attempt by putting fluorescent powder on both of their hands again and then perform hand wash with videos recorded. Digital images of hands will again be taken under UV light before and after hand wash. After washing hands, participants will scan fluorescent residual remained on their hands again in a hand scanner.

Participants will also be asked to fill in a questionnaire on knowledge and practice of hand hygiene as part of post-intervention assessment.

For the training purpose, after the completion of post-intervention measurements, the participants of the control group (Group D) will watch the training video and repeated hand washing and scanning for the third time if they agree. But the results of their third HW attempt will not be included into data analysis in this

Protocol  
Date 1 May 2023

study.

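### Nothing stated in the protocol keeps Groups B and D from seeing their UV-lit residual before the second wash, so the scanner-feedback contrast may be diluted

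*Protocol*

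**What the plan says.** The protocol sets out four arms: scanner feedback (A), video (B), both (C) and neither (D). The Background describes the scanner component as "a hand scanner used for students to immediately visualize the missing spots of hand hygiene", and its second objective is to "evaluate the effects of each component and collect feedbacks from participants".

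The Pre-intervention assessment is common to all arms. Powder goes on both hands, a UV image is taken at 365 nm, and the participant washes without instruction. Then: "After washing hands, participants will hold hands under UV light again to take digital image of hands". A scan in the hand scanner follows.

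The arms differ only after that. For Group A, "Participants will be informed about their hand scanner results of the first HW attempt to get individualized feedback about their hand wash performance"; Group C is also told its scanner results, and sees the video. Group B watches the video, "but they will not be informed about their hand scanner results". For Group D, "Participants will not be informed about the hand scanner results in the first HW attempt", and there is no video. Under Post-intervention assessment, "The participants will take the second HW attempt by putting fluorescent powder on both of their hands again".

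The section on randomization, allocation concealment and blinding says that participants are blinded, but gives no procedure that bears on the UV step.

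**The concern.** The restriction on Groups B and D covers the scanner's output. It does not cover what a participant may see when powder-marked hands are lit by UV light after washing. That sight, if available, is the same kind of information that the Background gives as the purpose of the scanner: where the wash missed. It would reach B and D before the wash on which they are assessed.

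The second objective needs the effect of each component. The scanner effect comes from A vs D and C vs B, or from A and C pooled against B and D. If residual is visible, all of these compare a scanner report plus UV viewing with UV viewing alone. Against the target of feedback versus no visual cue, they are pulled toward zero. What is at stake is a missed or understated scanner effect, not a false claim of benefit. B vs D stays balanced, but would mean video added to UV viewing, and the Group D heading, which describes a control without intervention, would not be strictly accurate.

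**Working it through.** **Timing and exposure.** Four UV images are taken per participant. Only one can do harm.

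- First attempt, before washing: the powder has just been applied, so the image says nothing about missed areas.
- First attempt, after washing: shows residual where the wash failed, in all arms, before the second attempt. This is the one that matters.
- Second attempt, before washing: powder has been reapplied, so again there is no information on missed areas.
- Second attempt, after washing: comes after the wash being assessed.

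For that one image, the protocol mentions no enclosure, curtain, eye cover or other means of hiding the hands from their owner. Nor does it say that the participant looks at them. Visibility is left open.

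**Size, on assumed inputs.** The protocol gives no effect size, SD, ICC, significance level or power, so there is no stated figure to reproduce. From Subject recruitment come about 280 students and "each session has 3 participants", with whole sessions assigned to one group. Assumed: full recruitment and equal arms (280/4 = 70), a true feedback effect of 0.5 SD against no visual cue, two-sided 5%, and ICC 0 to 0.10.

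Let f be the share of the feedback effect that UV viewing alone supplies, between 0 and 1. Group A gets the full effect and Group D gets f of it, so

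- expected A − D contrast: d = 0.5 × (1 − f)
- design effect: 1 + (3 − 1) × ICC
- effective n per arm: 70 / design effect
- power = Φ(d√(n/2) − 1.96) + Φ(−d√(n/2) − 1.96), with n the effective size

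Worked case, ICC 0.05: design effect 1.1, n = 70/1.1 = 63.6, √(63.6/2) = 5.64. At f = 0, 0.5 × 5.64 = 2.82 and power is Φ(0.86) = 80.5%. At f = 0.5, 0.25 × 5.64 = 1.41 and power is 29.2%.

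| Contrast | ICC | Effective n per side | f = 0 | f = 0.25 | f = 0.5 | f = 0.75 |
|---|---|---|---|---|---|---|
| A vs D | 0 | 70.0 | 84.1% | 60.2% | 31.6% | 11.5% |
| A vs D | 0.05 | 63.6 | 80.5% | 56.2% | 29.2% | 10.9% |
| A vs D | 0.10 | 58.3 | 77.0% | 52.6% | 27.1% | 10.4% |
| A+C vs B+D | 0.05 | 127.3 | 97.9% | 84.9% | 51.4% | 16.9% |

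The pooled row uses 140 per side and assumes the same f with and without video and no interaction. With a smaller assumed effect of 0.4 SD at ICC 0.05, A vs D gives about 62%, 39% and 20% at f = 0, 0.25 and 0.5, and the pooled contrast about 89%, 67% and 36%.

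The sample size needed to hold power grows as 1/(1 − f)²: 1/0.75² = 1.78 times at f = 0.25 and 1/0.5² = 4 times at f = 0.5. Pooling recovers power but not the estimate, which is still shrunk by the factor (1 − f).

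**The case against.** The strongest reply is that the defect is conditional. The protocol says that hands are held under UV light so that an image can be taken; it does not say that participants look at them. If the set-up hides the hands, f is near 0 and only a sentence is missing. The protocol also states its intent, by withholding scanner results from B and D and by saying that participants are blinded. This stands as a limit on confidence, but neither statement settles the matter: the first concerns the scanner and the second gives no means.

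A second reply is that the UV image is the same measurement step in all arms. The arms are defined by who is told scanner results and who sees the video, and for that contrast A vs D and C vs B are unbiased; Group D can be read as simply receiving neither. This is correct about internal validity. Dilution exists only relative to feedback against no visual cue, which the protocol does not name as its comparison. But the Background presents the scanner as the means by which students see missed areas, so a control that may see them already is a poor comparator for that component.

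A third reply is that the power figures rest wholly on assumed values. They do. They show how fast information is lost as f grows, not how large f is.

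Last, a shield could affect hand positioning and so the images, which also serve AI training and expert judgement, and hiding hands from their owner does not hide them from the other two participants in the session. Both are fair practical points for the design of the shield.

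**Conclusion.** The concern holds, with medium confidence. Followed as written, the protocol allows Groups B and D to see their missed areas before the second wash, and it describes nothing to prevent this. If they do see them, the scanner contrasts shrink by the factor (1 − f), and no analysis can recover the loss because no arm goes without the UV step. The amount is unknown and may be near zero. The conclusion assumes that seeing residual helps the next wash in the same direction as the scanner report, and that the report still adds something, as it should, since A and C are told an individual result. The randomised comparison stays valid; what changes is its meaning and its chance of showing an effect. This is a cheap improvement, not a fatal flaw. It belongs in the protocol because it concerns a procedure, not an analysis.

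**What to change.** In the Pre-intervention assessment, state that the first-attempt post-wash UV image is taken with the participant's view of the hands blocked by an enclosure or curtain, using the same set-up in all four arms. The shield should also cover the line of sight of the other participants in the session and leave the camera view clear; try this before recruitment starts. To carry out what the Group B and Group D sections already intend, state that the scanner display stays out of view of those groups until the second attempt is complete.

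If the view will not be blocked, define A vs D and C vs B as the effect of the scanner report added to UV viewing, define B vs D as video added to UV viewing, and do not describe Group D as receiving no intervention.

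The cost is a simple shield and one or two sentences; if the set-up already hides the hands, only the sentences. No extra visit, staff or measurement is needed. The drawback is a slightly slower photograph and some care with hand positioning.
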